### **4.3 Study Treatment Phase**

#### **4.3.1 Intervention condition**

Sleep Well! will be provided over approximately 6-8 weeks, to allow for families to reschedule sessions as needed, and will include 3 sessions. Intervention sessions will typically last about an hour, but session length may vary. Content is delivered in a modular format based on family goals and the child's sleep concern (e.g., using electronics before bedtime; an inconsistent bedtime routine; etc.). To ensure high-quality care, intervention providers will receive regular supervision. Providers will also contact families by phone between sessions (3 times total) to (a) promote attendance, engagement, and implementation of Sleep Well! strategies, (b) assist in resolving barriers to treatment, and (c) guide families to community resources as needed. As noted above (3.1.2), text messages about the intervention will also be sent to families via Twilio and its integration with REDCap. For ethical reasons, families will be informed that they have the right not to participate in the study. If they choose not to participate, they will be referred to their pediatrician, who may provide the family with additional referrals to the CHOP Sleep Center or other behavioral health services, consistent with the current standard of care at CHOP.

Intervention sessions that occur in-person, via HIPAA-compliant video, or by telephone will be audio-recorded to monitor fidelity. Telephone check-in calls will not be audio-recorded. After each intervention session and intervention-related phone call, the interventionist will document which intervention contents were used using an intervention-specific fidelity checklist. The study interventionist will also document any feedback regarding the intervention as a method to assess intervention feasibility and usability. In addition, approximately 2 weeks into the intervention phase caregivers will complete a brief survey about their child's sleep electronically via REDCap (mid-point assessment).

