#### **4.3.2 Procedures for training Sleep Well! interventionists**

[name], a licensed psychologist who is also a Diplomat in Behavioral Sleep Medicine, will train and supervise all study interventionists, who are doctoral-level or post-doctoral level clinical psychology trainees at CHOP. [name] will provide each interventionist with approximately 8 hours of training prior to intervention. Interventionists will be trained to implement the treatment manual and attend to process variables, including establishing trust, listening actively, and re-directing tangential comments. All interventionists are mandated child abuse reporters and will be trained to identify and report child abuse and any other concerns related to participant safety. Consultation and peer supervision related to intervention delivery will occur weekly with [name] mentor, [name], Associate Director of the CHOP Sleep Center and Diplomat in Behavioral Sleep Medicine.

---

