### 4.3.3 Control (enhanced usual care) condition

The enhanced usual care condition will occur for between 6 and 8 weeks. At randomization to this condition, participants will be provided with an evidence-based sleep guidelines for young children. These guidelines are summarized in the CHOP Parent Family Education manual and have been reviewed and approved by pediatric sleep experts (including study Co-I [name] and co-I [name]) and CHOP primary care physicians. Participants in this condition will also be able to consult with their primary care physician for management of child sleep. Consistent with usual care in the CHOP system, the primary care physician may manage the sleep concern or choose to make a referral to the CHOP sleep center or to other behavioral health services internal or external to the CHOP system. Of note, the CHOP Parent Family Education handouts provide contact information for the CHOP Sleep Center and direct readers to follow-up with their primary care provider for further guidance.

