For qualitative interview data, transcribed interviews will be coded by study team members using an iterative process that begins with open coding, codebook development and refinement, and consensus regarding the codes. We will use an integrated approach, with a priori codes based on prior work and themes emerging from the data. Once a stable codebook is developed, approximately 20% of the data will be double coded for reliability purposes (weighted kappa). Separate codebooks may be developed for the Sleep Well! participant interviews and for the enhanced usual care condition interviews. We will also explore how themes from the intervention group vary by quantitative caregiver-reported outcome data (e.g., sleep problem perception) and family factors (e.g., shiftwork). We will also examine variation using this method for the usual care group interviews.

Data analysis for the secondary sleep outcomes (below) will include (1) the application of mixed effects growth models, and (2) generating effect sizes, as follows.

- (1) Mixed effects linear growth models will also be applied to compare overall change in continuous outcomes between groups from pre-intervention to follow-up using an intent to treat approach with maximum likelihood estimation. Individual variability in the outcomes from pre-intervention through the follow-up assessments will be predicted by a two-level fixed effect condition variable (coded 0 for enhanced usual

care and 1 for intervention), a time variable with the intercept defined as the pre-intervention assessment and weeks between this assessment and last follow-up, and the group  $\times$  time interaction. Models will account for random effects (intercept, time) and fixed effects (group, and time by group). The time by intervention group interaction identifies whether there is a significant between-group difference in change since pre-intervention. Categorical outcomes will be modeled as mixed-effects growth models with maximum likelihood and a logit link. Model parameters include those described for the continuous models and a threshold parameter at each timepoint. Any sleep and behavior outcomes that are significantly different by group at pre-intervention will be included as covariates in all models.

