## 6.5 Sample Size and Power

As is appropriate for a pilot study, the primary goal of this study to estimate effect sizes to fully power a future large-scale randomized controlled trial of the adapted behavioral sleep intervention through a subsequent R01 submission. However, we will have adequate power to detect the expected medium effects (found in similar efficacy and effectiveness trials for sleep) between groups on sleep outcomes. Based on previous primary care behavioral intervention research studies conducted at CHOP, we expect an approximate attrition rate of 15% at follow-up. A final sample size of 68 participants yields  $>80\%$  power to detect medium (0.5 SD) between-group effects using linear regression and adjusting for covariates (pre-intervention scores; socio-demographic variables) to evaluate change in sleep outcomes. The proposed sample of 80 dyads is thus sufficient for detecting medium intervention effects and accounts for potential attrition. Medium effects for relevant child sleep outcomes are equivalent to a  $\sim$ 10-minute reduction in sleep onset latency, a 30 to 40-minute increase in sleep duration, and a reduction of  $\sim$ 1 night awakening—all clinically meaningful results.

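### The growth models leave out interventionist clustering in the Sleep Well! arm; if it exists, condition x time standard errors are too small, and a fixed-ICC sensitivity analysis is a cheap safeguard.

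*Combined protocol and SAP*

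**What the plan says.** The combined protocol and SAP describes delivery that differs in structure between the arms.

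- **Sleep Well! arm.** Section 4.3.2 says a licensed psychologist "will train and supervise all study interventionists, who are doctoral-level or post-doctoral level clinical psychology trainees at CHOP". Section 4.3.1 gives each family 3 sessions, and "Providers will also contact families by phone between sessions (3 times total"). No number of interventionists is given, and no rule says how families are assigned to them.
- **Control arm.** Under section 4.3.3, "participants will be provided with an evidence-based sleep guidelines for young children", with usual primary care available. No study interventionist is involved.
- **Model.** Section 6.4 fits mixed-effects growth models "using an intent to treat approach with maximum likelihood estimation". On the structure it says: "Models will account for random effects (intercept, time) and fixed effects (group, and time by group"). On the test it says: "The time by intervention group interaction identifies whether there is a significant between-group difference in change since pre-intervention". The same approach serves the sleep and behavior outcomes and the exploratory ones, with a logit link for categorical outcomes.
- **Sample size.** Section 6.5 states: "A final sample size of 68 participants yields" more than 80% power "to detect medium (0.5 SD) between-group effects using linear regression and adjusting for covariates (pre-intervention scores; socio-demographic variables"). It contains no design effect.

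No section mentions an interventionist effect, cluster-robust errors or an ICC.

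**The concern.** This is a partially nested design, with a grouping factor above the family in one arm only. Interventionists differ in skill and style, content is modular, and contact is repeated. Families who share an interventionist may therefore change more alike than families who do not. The section 6.4 model has random effects for the dyad only and so treats all Sleep Well! dyads as independent. The relevant quantity is the ICC of change, because randomization and baseline precede any interventionist contact.

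If that ICC is positive, the variance of the mean change in the Sleep Well! arm is understated. The condition x time intervals are then too narrow and the p-values too small. This matters for two uses that section 6.5 makes of the results: the claim that the trial can detect between-group sleep effects, and the use of its effect sizes to plan a larger trial.

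**Working it through.** **Inputs.** From section 6.5: 80 dyads enrolled, 15% attrition, 68 analysed, effect 0.5 SD. Assumed because not stated: 1:1 allocation (34 per arm), two-sided alpha 0.05, equal caseloads, k = 2, 4 or 8 interventionists, ICC = 0.02, 0.05 or 0.10, and equal total variance in the two arms.

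**The plan's own figures.** The attrition step reproduces: 80 x 0.85 = 68. The power above 80% cannot be confirmed from the stated inputs. With 34 per arm and 0.5 SD, an unadjusted two-sided t-test has 53% power, and covariate adjustment reaches 80% only if the covariates correlate about 0.69 with the outcome. No correlation is stated. That is a separate matter, but no variant tried includes interventionist clustering.

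**Effect of clustering alone.** With balanced visits, the condition x time test is a two-sample comparison of dyad-level change.

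- Families per interventionist: m = 34/k.
- Design effect in the Sleep Well! arm: DE = 1 + (m - 1) x ICC.
- True over assumed variance of the group difference: V = (DE + 1)/2, since only one arm is clustered.
- True two-sided alpha: 2 x [1 - Phi(1.96/sqrt(V))].

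Worked case, k = 4 and ICC 0.05: m = 8.5; DE = 1 + 7.5 x 0.05 = 1.375; V = 2.375/2 = 1.1875; sqrt(V) = 1.090; alpha = 2 x [1 - Phi(1.799)] = 7.2%. The model's standard error is 1/1.090 = 0.918 of the correct one, or 8% too small.

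| k | m | V at ICC 0.02 / 0.05 / 0.10 | True alpha | Interval widening needed, sqrt(V) - 1 |
|---|---|---|---|---|
| 2 | 17 | 1.160 / 1.400 / 1.800 | 6.9% / 9.8% / 14.4% | 8% / 18% / 34% |
| 4 | 8.5 | 1.075 / 1.188 / 1.375 | 5.9% / 7.2% / 9.5% | 4% / 9% / 17% |
| 8 | 4.25 | 1.033 / 1.081 / 1.163 | 5.4% / 5.9% / 6.9% | 2% / 4% / 8% |

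A simulation of dyad-level change scores (20,000 trials per cell) agrees: 7.6% for k = 4 and 9.8% for k = 2, both at ICC 0.05.

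**Maximum likelihood, kept separate.** If ML is paired with z-tests, the test is mildly liberal without any clustering: P(|t66| > 1.96 x sqrt(66/68)) = 5.8%. Section 6.4 names no reference distribution, so this is conditional. The table excludes it.

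**Price of estimating the interventionist variance.** With DE as above, the Satterthwaite degrees of freedom are (DE + 1)^2 / [DE^2/(k - 1) + 1/33]. Interval width relative to the unclustered z interval is sqrt(V) x t/1.96. At ICC 0.05:

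- k = 4: df = 2.375^2 / (1.375^2/3 + 1/33) = 8.5; t = 2.28; width ratio 1.27, or 27% wider.
- k = 2: df = 2.8^2 / (1.8^2 + 1/33) = 2.4; t = 3.69; width ratio 2.23, or 123% wider.

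**The case against.** The strongest reply is that the documents do not show that any harm occurs. A reader might infer a small pool of interventionists, standard errors that are certainly too small, and significance that is certainly overstated. None of this is stated. With 8 interventionists and an ICC of 0.02, alpha is 5.4%; with an ICC of zero there is no inflation. Training to a manual, weekly supervision and fidelity coding (sections 4.3.2 and 5.2) aim at uniform delivery, which argues for a low ICC without proving it is zero. Nor do the documents say that each family keeps one interventionist throughout. All of this stands, and the point has to be conditional.

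The scope is also limited. Primary outcomes are descriptive, so only secondary and exploratory models in a pilot are touched, and the effect estimates themselves are not biased. That stands too.

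The arithmetic simplifies the planned model. Section 3.1 gives the mid-point sleep assessment to the intervention arm only, visit weeks vary, likelihood-based intent-to-treat analysis uses partial data from dyads who drop out, and categorical outcomes use a logit link. The table is therefore indicative.

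Finally, it is tempting to prescribe an estimated interventionist random slope and call the cost slight. With few interventionists it is not, as the widths above show. With 4 interventionists and a true ICC of 0.05, an ANOVA estimate of the ICC would be zero or negative about 44% of the time. A reader might also expect this pilot to supply the ICC for the next trial; with so few interventionists it could give only an imprecise value.

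What survives is the omission and its direction. No section allows for interventionist correlation, and any positive ICC of change makes the intervals too narrow.

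**Conclusion.** The point holds as a conditional one and is best treated as a cheap improvement. Interventionists exist in one arm only, and the section 6.4 model omits them. The true error rate of a nominal 5% condition x time test then ranges from about 5.4% (8 interventionists, ICC 0.02) to 14.4% (2 interventionists, ICC 0.10), with 7.2% for 4 interventionists at ICC 0.05. These figures rest on 34 per arm, 1:1 allocation, equal caseloads, one interventionist per family and balanced visits. The number of interventionists and the ICC are assumptions throughout. The documents do not support saying that significance is overstated as a matter of fact.

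**What to change.** Amend section 6.4 as follows.

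1. Carry the interventionist ID into the analysis file, and report the number of interventionists and their caseloads.
2. Fit continuous outcomes with REML and Satterthwaite or Kenward-Roger degrees of freedom.
3. Add a sensitivity analysis giving condition x time intervals with the Sleep Well!-arm interventionist ICC of change fixed at 0.02, 0.05 and 0.10. REML and these degrees-of-freedom methods do not carry over directly to the logit models, so apply the same design-effect inflation to those intervals.
4. Fit an estimated interventionist random slope, in the Sleep Well! arm only, if there are enough interventionists to support it. State the minimum number in advance, and report any ICC estimate as imprecise.

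The cost is SAP wording and one extra variable; interventionists already complete a checklist after each session and call (section 4.3.1). The statistical price is wider intervals. In the fixed-ICC analysis this is modest, for example 4% to 17% with 4 interventionists. It is substantial if the variance is estimated from few interventionists: about 27% with 4 and more than double the width with 2, at ICC 0.05.

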## 8 STUDY ADMINISTRATION

### 8.1 Treatment Assignment Methods

#### 8.1.1 Randomization

Participants will be randomly assigned to the intervention or enhanced usual care condition at the baseline assessment. The randomization sequence will be generated by a study statistician. Randomization will be maintained by keeping a separate, password-protected list in REDCap that lists subject ID and group assignment.

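### The 6.4 growth model leaves the baseline group difference free, so its group × time test works like a change score and uses the baseline less efficiently than the adjusted analysis behind 6.5

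*Combined protocol and SAP*

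**What the plan says.** Section 6.4 (Statistical Methods) analyses the continuous sleep and behaviour outcomes with mixed-effects growth models fitted by maximum likelihood. The predictors include condition (0/1) and "a time variable with the intercept defined as the pre-intervention assessment". On the terms, it says: "Models will account for random effects (intercept, time) and fixed effects (group, and time by group". The inferential test is the group × time interaction, read as the between-group difference in change since baseline, and the effect sizes are drawn from the same model. A baseline value enters as a covariate only if it differs significantly between arms.

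Section 6.5 (Sample Size and Power) rests on a different analysis. It says "A final sample size of 68 participants yields" more than 80% power "to detect medium (0.5 SD) between-group effects using linear regression and adjusting for covariates (pre-intervention scores; socio-demographic variables". On losses, "we expect an approximate attrition rate of 15% at follow-up", and it concludes: "The proposed sample of 80 dyads is thus sufficient for detecting medium intervention effects and accounts for potential attrition".

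On timing, 8.1.1 says: "Participants will be randomly assigned to the intervention or enhanced usual care condition at the baseline assessment". It does not say whether the baseline measures come before or after assignment. Section 3.1 names random assignment and then completion of baseline measures. Section 4.2 lists the questionnaires, then randomisation, then the 7-day diary and actigraphy.

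**The concern.** With time zero at baseline, the group coefficient is the difference between arms before treatment. For a measure taken before assignment, randomisation makes that difference zero in expectation. Estimating it anyway means that a chance baseline imbalance is subtracted from the result at about full weight, as in a change score. Baseline adjustment, or a baseline mean shared by the arms, subtracts only the part that the correlation between visits supports.

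The secondary objective depends on this term. So do the effect sizes, which 6.5 describes as the main purpose of the pilot. With about 34 dyads per arm, chance imbalance is not negligible. The covariate rule in 6.4 does not repair this. If tested at the 5% level, it would be triggered in about 5% of outcomes under randomisation, and a covariate main effect leaves the group × time contrast essentially unchanged.

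**Working it through.** **Inputs from the plan.** 68 analysed, 80 enrolled, 15% attrition, effect 0.5 SD (6.5); model terms (6.4); post-intervention at weeks 9–16 and follow-up at weeks 15–24 (3.1).

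**Assumptions, not in the plan.** Allocation 1:1 (34 per arm); two-sided 0.05; visits at weeks 0, 11 and 18; baseline SD 1; linear effect reaching 0.5 SD at week 18. ρ is the random-intercept share of baseline variance, which equals the between-visit correlation when there is no random-slope variance. s is the random-slope variance at week 18, uncorrelated with the intercept. The mid-point sleep survey, which 3.1 gives to the intervention arm only, is left out.

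**The plan's own figure.** 68/0.85 = 80, so the attrition step reproduces. The power does not follow from the stated inputs alone. Unadjusted, SE = √(2/34) = 0.243 and power is 53% (t) or 54% (normal). With baseline adjustment, the variance is (2/34)(1 − r²). At r = 0.68, SE = √(0.0588 × 0.538) = 0.178 and power is Φ(0.5/0.178 − 1.96) = 80%. The claim therefore needs a correlation of about 0.68 to 0.70, which is not stated.

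**Free group term (6.4).** Put time on a 0–1 scale: x = (0, 0.611, 1), with mean 0.537. The sum of squared deviations is 0.288 + 0.005 + 0.214 = 0.508. Under this covariance the estimate is the difference in ordinary slopes, with weights −1.06, 0.15 and 0.91 on the three visits. The baseline difference is thus subtracted at slightly more than full weight. The variance is (2/34)[(1 − ρ)/0.508 + s]. A pure change score has (2/34)[2(1 − ρ) + s]. With s = 0 the ratio is 1/(2 × 0.508) = 0.98.

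**Common baseline mean.** The variance is (2/34)[1/q + s], where q = [Σx² − ρ(Σx)²/(1 + 2ρ)]/(1 − ρ), Σx² = 1.373 and (Σx)² = 2.596.

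Example, ρ = 0.5 and s = 0. Free: 0.0588 × 0.5/0.508 = 0.0579, SE 0.241. Shared: q = (1.373 − 0.649)/0.5 = 1.449, variance 0.0588/1.449 = 0.0406, SE 0.201. The variance falls by 30%.

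Power in percent, free → shared (loss in points, from unrounded values), noncentral t with 66 df:

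| ρ | s = 0 | s = 0.2 | s = 0.4 | s = 0.6 |
|---|---|---|---|---|
| 0.3 | 41.0 → 62.8 (21.8) | 36.6 → 53.3 (16.7) | 33.2 → 46.1 (13.0) | 30.4 → 40.7 (10.3) |
| 0.4 | 46.4 → 64.8 (18.4) | 40.9 → 54.8 (13.9) | 36.6 → 47.3 (10.7) | 33.1 → 41.6 (8.4) |
| 0.5 | 53.5 → 68.6 (15.1) | 46.3 → 57.7 (11.4) | 40.8 → 49.4 (8.6) | 36.5 → 43.2 (6.7) |
| 0.6 | 62.9 → 74.5 (11.6) | 53.4 → 62.2 (8.8) | 46.2 → 52.8 (6.6) | 40.7 → 45.8 (5.1) |
| 0.68 | 72.6 → 81.1 (8.5) | 60.7 → 67.3 (6.6) | 51.7 → 56.7 (5.0) | 44.9 → 48.7 (3.8) |
| 0.8 | 89.9 → 93.1 (3.2) | 75.1 → 78.4 (3.3) | 62.6 → 65.1 (2.6) | 53.1 → 55.0 (1.9) |

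Slope variance adds the same amount to both variances, so the relative gain shrinks as s grows.

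**Sensitivity at ρ = 0.5, s = 0 (normal approximation).** Weeks 0/12/20 give a loss of 15.0 points and weeks 0/16/24 give 15.8. Simulated maximum-likelihood fits (random intercept only, weeks 0/12/20) gave 53% against 70%. If the effect is already complete at post-intervention and then holds, the loss at weeks 0/12/20 is larger: 19.6 points at ρ = 0.5 and 10.0 at ρ = 0.68.

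**The case against.** A model with group, time and group × time is conventional, and its interaction estimate is unbiased under randomisation. A reader might infer that the 6.4 analysis is wrong or biased. The documents do not support that: chance imbalance adds variance, not bias.

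A reader might also take one fixed loss, for example 9 to 18 points, as a property of the plan. With no random slope, that range fits only ρ of about 0.4 to 0.65. The plan states no correlation and no slope variance, and 6.4 does include a random time effect, which lowers the loss.

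The strongest objection concerns the premise of a shared baseline mean. Read literally, 3.1 puts assignment before all baseline measures, while 4.2 puts it after the questionnaires but before diary and actigraphy. Families are not blinded (8.1.2), and controls receive the sleep guidelines at randomisation (4.3.3). If caregivers know their arm when they rate the child, the arms need not share a baseline mean. Forcing one could then bias the estimate, whereas the planned model allows for the difference. This objection stands. It rules out applying the point to every outcome and makes the remedy conditional. The primary endpoints are also unaffected: they are feasibility and acceptability, analysed descriptively.

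**Conclusion.** The point holds as a matter of efficiency. The 6.4 test is in effect a change-score test (variance ratio about 0.98 in the setting above) and does not match the baseline-adjusted analysis that 6.5 uses for power. The cost is precision on secondary outcomes and on the effect sizes for the next trial.

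Under the stated assumptions the loss is about 3 to 22 points for ρ from 0.8 down to 0.3 with no slope variance, and about 2 to 17 points with slope variance 0.2 to 0.6. At ρ = 0.68 it is about 4 to 8.5 points. These figures are for continuous outcomes with a linear effect; the logit models were not calculated.

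A reader might infer that a common baseline mean secures the 80% power claimed in 6.5. At ρ = 0.68 it does so only with little or no slope variance (81% at s = 0, 67% at s = 0.2).

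**What to change.** 1. Reconcile 3.1 and 4.2 on whether the Brief Child Sleep Questionnaire and the Child Behavior Checklist are completed before assignment, and state the order for diary and actigraphy.
2. In 6.4, for outcomes whose baseline is completed before assignment, drop the group main effect at the pre-intervention visit so that both arms share one baseline mean. Keep time, group × time and the random effects. Report the free-group model as a sensitivity analysis.
3. Keep the free-group model for actigraphy and any other baseline collected after assignment, unless the documents establish that it precedes assignment.

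The cost is one model term and a few lines of text, with no new data. The small downside is that the constraint is valid only for baselines taken before assignment, so the analysis will differ between outcomes if the order does.

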- (2) Effect sizes for the magnitude of group differences will be drawn from the mixed effects models. The effect size for the condition  $\times$  time interaction is equivalent to Cohen's d-statistic. For categorical outcomes, percent change in the odds for the condition  $\times$  time interactions are provided as a measure of effect size.

Secondary sleep outcomes for these analyses will be drawn from the caregiver-rated Brief Child Sleep Questionnaire (BCSQ) and actigraphy (objective sleep measurement) and will include:

- Child sleep problems (BCSQ)
- Child bedtime resistance (also called "bedtime difficulties" BCSQ)
- Child sleep onset latency (BCSQ)
- Child night awakenings (frequency and duration BCSQ)
- Child sleep quality (BCSQ)
- Child total (BCSQ) and nighttime sleep duration (BCSQ and sleep onset to offset for actigraphy)

To examine secondary child behavior outcomes, we will examine change by group over time from pre-intervention to follow-up, exactly as described for the sleep outcomes (see above).

Secondary behavior outcomes drawn from validated the following validated clinical measures include:

- Child externalizing problems composite T-score (Child Behavioral Checklist for ages 1.5-5 years)
- Child internalizing problems composite T-score (Child Behavioral Checklist for ages 1.5-5 years)

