#### Additional exploratory analyses

Using the above growth model methods for secondary child sleep and behavior outcomes, we will also explore change in other sleep outcomes (BCSQ), including child bedtime routine consistency and sleep health behaviors (caffeine, fussy morning mood, bedtime fears, insufficient sleep) on the BCSQ and caregiver mood (CES-D) and sleep (PROMIS).

Exploratory analyses included tests of moderating effects for age of the child, whether the caregiver reported shift work, pretest measure of parent mood (CES-D), and pretest measure

of parent sleep (PROMIS). Moderation models will be run separately for each moderator and include main effects of the moderator and all higher order interaction terms with condition, time, and condition  $\times$  time.

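### Section 6.4 reads 11 secondary outcomes by significance with no lead outcome, alpha or adjustment, and 6.5 claims power to detect sleep effects, although the stated aim is estimation

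*Combined protocol and SAP*

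**What the plan says.** Section 6.4 opens the secondary analysis with two parts: "Data analysis for the secondary sleep outcomes (below) will include (1) the application of mixed effects growth models, and (2) generating effect sizes". In the first part, each outcome has its own model with group, time and group-by-time terms, and the plan explains how the last is read: "The time by intervention group interaction identifies whether there is a significant between-group difference in change since pre-intervention". In the second part, effect sizes are taken from the same models. Intervals are not mentioned.

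On the outcomes, 6.4 states: "Secondary sleep outcomes for these analyses will be drawn from the caregiver-rated Brief Child Sleep Questionnaire", together with actigraphy. Six bullets follow, two of which hold more than one measure. Two Child Behavior Checklist composites are then added and analysed in the same way as sleep.

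Under Additional exploratory analyses, the same models are applied to further sleep-health and caregiver measures, and four moderators are examined: "Moderation models will be run separately for each moderator".

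Other sections frame these outcomes in different ways:

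- 6.2 defines the secondary endpoints as the size and direction of change.
- 2.2 sets out to compare the arms on sleep, but only to explore behavior.
- 6.5 first says that the main goal is to estimate effect sizes for a later, fully powered trial. Its next sentence claims sufficient power for medium between-group effects on sleep outcomes, without saying which.

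No section names a lead secondary outcome, a significance level, a testing order or a multiplicity adjustment.

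**The concern.** A plan that estimates effects needs no control of multiple tests. A plan that tests for significance and claims power does need to say which test carries the conclusion. This plan does some of each. With 11 tests, no lead and no stated level, the text does not prevent a report from resting an efficacy statement on whichever interaction is significant. A reader of that report could not tell a planned main result from the best of 11.

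The primary endpoints are not affected. They are feasibility and acceptability measures, analysed descriptively (6.1, 6.4). What is at stake is how the secondary sleep and behavior results can be interpreted, and how far they can be relied on when the later trial is planned.

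**Working it through.** **The plan's own figure.** The documents state no family-wise error rate to reproduce. The sample size in 6.5 does reproduce: 68 completers with 15% attrition gives 68 / (1 − 0.15) = 80 dyads. That calculation concerns one comparison at a time and says nothing about several outcomes.

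**Count of outcomes, from the lists in 6.4.**

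- Sleep problems, bedtime resistance, sleep onset latency: 3
- Night awakenings, frequency and duration: 2
- Sleep quality: 1
- Duration (questionnaire total, questionnaire nighttime, actigraphy nighttime): 3
- Externalizing and internalizing T-scores: 2

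Sleep gives 3 + 2 + 1 + 3 = 9. With behavior, 9 + 2 = 11. Each has one group-by-time test.

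**Assumptions that the documents do not supply.** Each test is two-sided at 0.05. There is no true effect on any outcome. The test statistics are approximately normal with a common correlation ρ, shown over a range.

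**Independent outcomes.** The chance of at least one significant result is 1 − (1 − 0.05)^m.

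- m = 11: 1 − 0.95^11 = 0.431
- m = 9: 1 − 0.95^9 = 0.370

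**Correlated outcomes.** With c = 1.96, the chance is

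1 − ∫ φ(t) [Φ((c − √ρ t)/√(1 − ρ)) − Φ((−c − √ρ t)/√(1 − ρ))]^m dt.

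| ρ | All 11 | Nine sleep measures only |
|---|---|---|
| 0 | 43.1% | 37.0% |
| 0.3 | 37.5% | 32.6% |
| 0.5 | 30.4% | 26.9% |
| 0.7 | 22.3% | 20.2% |
| 0.9 | 13.1% | 12.4% |

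**Unequal correlation.** Eight of the 11 measures come from one caregiver questionnaire, so a block pattern is more realistic than a common ρ. In simulation, correlation of 0.3 to 0.7 within the questionnaire, 0.5 to 0.7 between the two behavior scores and 0.1 to 0.3 across blocks gave 39% down to 28%.

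**Sensitivity to the count.** Counting bullets instead of measures gives 6 + 2 = 8, and 1 − 0.95^8 = 34% under independence.

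**The case against.** The strongest reply is that this is a pilot, and that its secondary analysis is already mostly estimation. Section 6.2 speaks of size and direction of change, 6.4 commits to effect sizes from every model, 6.5 names effect-size estimation as the main goal, and 2.2 only explores behavior. On this view the significance sentence merely explains a model term, and formal adjustment of secondary outcomes in a pilot is a matter of convention.

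Much of this stands, and it is why mandatory adjustment is not the remedy. Bonferroni over 11 outcomes means 0.05 / 11 = 0.0045 per test. With 34 per arm (equal allocation assumed), power for 0.5 SD would be about 22% without covariates, or about 53% if covariates explained half the variance. The reply does not remove the mixed message, though. The significance sentence applies to every outcome, 2.2 sets out to compare the arms on sleep, and the power claim in 6.5 is confirmatory in tone.

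Three stronger readings are tempting, and the documents do not support them:

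- A reader might infer that a false positive is likely. Every figure for the 11 outcomes is below 50%. Nor is 30% a lower limit, because the rate keeps falling as correlation rises.
- A reader might infer that the largest observed effect will be used to size the later trial. Section 6.5 says that effect sizes will inform that trial, but not which one or how it is chosen.
- A reader might multiply four moderators by 11 outcomes and count 44 moderator tests. The plan does not say which outcomes the moderator models cover, and it already labels them exploratory.

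**Conclusion.** The point holds as an inconsistency between the estimation aim and the testing language, with a real but bounded cost. If each of the 11 interactions is read at two-sided 0.05 and the intervention has no effect on any outcome, the chance of at least one significant result runs from 43% (independence) to 13% (correlation 0.9). For the nine sleep measures alone, the range is 37% to 12%. All of these exceed 5%. They rest on an assumed alpha and assumed correlations, and on inferring from the plan's silence that no adjustment is intended.

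The primary feasibility and acceptability results are unaffected. This is a low-cost improvement that decides what may be concluded from the secondary results; it is not a flaw in the design.

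**What to change.** In 6.4, replace the sentence that reads the interaction by significance with wording such as: *The group-by-time effects for all 11 secondary outcomes will be reported together, each with a 95% confidence interval. No single secondary p-value will be taken to support a conclusion of efficacy.* Add that exploratory and moderator results are reported as estimates only, without significance language.

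In 6.5, reword the power claim, and the closing statement that 80 dyads suffice to detect medium effects, so that both agree with the estimation goal. If 6.4 is changed alone, the two sections will still disagree.

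If p-values are shown, Benjamini-Hochberg values across the 11 may be given beside them. This is optional.

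The change is to wording only. It needs no extra participants, visits or measures. The downside is that fewer results can be labelled significant.
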